### 7.3. Sample Size Determination

A total of 240 veterans and active-duty service members will be enrolled (consented) into the study so that even with attrition of up to 50% of study subjects, we can ensure that the study is completed by a MINIMUM of  $n = 120$  participants (60 in each arm) to reach 90% power for rejecting the null hypothesis under the targeted benefit of  $\delta = \mu_{\text{Active}} - \mu_{\text{Sham}} = 3$  points with an equal standard deviation of  $\sigma = 5$  points in each of the two arms. Figure 1 (see below) depicts the power of the trial as a function of the true standardized reduction ( $\delta/\sigma$ ) in the population assuming we enroll and **retain** a MINIMUM of 60 participants in each arm of the proposed trial. If we get more than 60 participants (i.e. less than a 50% attrition rate) this will just make the study results even more powerful.

**Figure 4: Power Curve (total completers-  $n=120$ , 50% for each arm)**

The rationale for powering the trial to detect a 3-point reduction is two-fold. First, a 3-point reduction constitutes a clinically relevant benefit as this may reflect, for example, a change from 3 (most severe) to 0 (least severe) on a particular item of the PSQI, or a 1-point reduction on three items of the PSQI. Second, assuming a 5-point standard deviation, the targeted 3-point reduction is equivalent to a 0.6 standardized effect, which is plausible as evidenced by a meta-analysis for the observed benefit in previous clinical trials evaluating cognitive behavioral therapies for treating nightmare disorder using the difference between PSQI score at baseline and post-treatment follow-up assessment in which the estimated standard effect size was estimated to be 0.68 (0.34, 1.03). Furthermore, a more recent open-label trial reported a standardized effect size of 1.06. Therefore, the targeted 3-point reduction or 0.6 standardized effect constitutes both a plausible and clinically meaningful benefit in this context.

#### **7.4. Interim Monitoring**

The trial will incorporate two interim analyses after 20 and 40 participants in each arm have completed the first 30 days of the trial. Statistical monitoring guidelines will be based on two-sided O'Brien-Fleming boundaries. This conservative interim monitoring plan demands a negligible increase in sample size, so with a MINIMUM of 120 total participants completing, the trial will still be powered at 90% for the targeted benefit. The interim analyses will assess only patient demographics and primary endpoint.

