## 7.2. Statistical Hypothesis Testing

The primary hypothesis is that NW will improve sleep quality as measured by the Pittsburgh Sleep Quality index (PSQI) relative to sham. On average, compared to the sham, NW will provide a greater reduction in PSQI score measured on day 30 relative to baseline on day 0

Let  $Y_{ij}$  denote the PSQI score for the  $i$ -th participant at their  $j$ -th assessment,  $j=0,1,2$ , where  $j=0$  denotes baseline, and  $i=1,\dots,n$ . Let  $D_i = Y_{i0} - Y_{i1}/2$ , i.e., the difference between the  $i$ -th participant's PSQI score at baseline ( $Y_{i0}$ ) and their average PSQI score across the post-treatment initiation assessment ( $Y_{i1}$ ). The trial will test the hypotheses

$$H_0: \mu_{\text{Active}} \leq \mu_{\text{Sham}} \text{ versus } H_A: \mu_{\text{Active}} > \mu_{\text{Sham}},$$

where  $\mu_{\text{Active}}$  and  $\mu_{\text{Sham}}$  respectively reflect the average difference with NW and sham.

We will evaluate the statistical hypotheses using an equal-variances, two sample t-test. If the equal variance assumption is untenable, we instead will use an unequal-variances, two sample t-test, i.e., Welch's t-test. We will reject the null hypothesis ( $H_0$ ) that change in PSQI from baseline to day 30 resulting from the active NW system is no better than sham when the two-sided p-value is less than or

equal to 0.05 and the direction of the difference favors NW over sham. In this way, the proposed test controls the one-sided type I error rate at 2.5%.

Data will be presented as mean(standard deviation) or median (interquartile range), as appropriate for continuous variables. Categorical variables will be presented as frequency (percentage). Continuous data will be assessed for normality, and transformed as appropriate (e.g. log transformation, square root transformation, etc.). Patient demographics and characteristics will be listed and compared.

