## **12. Study Discontinuation and Closure**

This study may be temporarily suspended or prematurely terminated if there is sufficient reasonable cause. Written notification, documenting the reason for study suspension or termination, will be provided by the suspending or terminating party to the principal investigator and study sponsor (if sponsor is NOT the terminating party). If the study is prematurely terminated or suspended, the Principal Investigator (PI) will promptly inform study participants, and, as necessary, the Institutional Review Board (IRB), and/or the sponsor and will provide the reason(s) for the termination or suspension. Study participants will be contacted, as applicable, and be informed of changes to their study visit schedule.

terminate

Circumstances that may warrant termination or suspension include, but are not limited to:

- Determination of unexpected, significant, or unacceptable risk to participants
- Demonstration of efficacy that would warrant stopping
- Insufficient compliance to protocol requirements
- Data that are not sufficiently complete and/or evaluable
- Determination that the primary endpoint has been met
- Determination of futility

Study may resume once concerns about safety, protocol compliance, and data quality are addressed, and satisfy the sponsor, IRB and/or Food and Drug Administration (FDA).

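### The plan allows a stop for benefit at 20 or 40 completers per arm but has no rule for estimating the PSQI difference after a stop or for participants still in follow-up, so the ordinary difference would on average be too large

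*Protocol*

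**What the plan says.** - **Looks.** Protocol Section 7.4: "The trial will incorporate two interim analyses after 20 and 40 participants in each arm have completed the first 30 days of the trial". The looks cover demographics and the primary endpoint. They use two-sided O'Brien-Fleming boundaries, which the section calls guidelines and for which it gives no numerical limits.
- **Authority to stop.** Section 7.4 itself contains no stopping instruction. It comes from Section 12, whose list of possible grounds for termination includes "Demonstration of efficacy that would warrant stopping", and also the primary endpoint having been reached.
- **Primary analysis.** Section 7.2: "We will evaluate the statistical hypotheses using an equal-variances, two sample t-test", with Welch's version if variances differ. On summaries it says "Data will be presented as mean(standard deviation) or median (interquartile range), as appropriate for continuous variables". It also leaves room for transformation, a rank test and repeated-measures methods. None of these accounts for the interim looks.
- **Yardstick.** Section 7.3 gives as a reason for the powering that "a 3-point reduction constitutes a clinically relevant benefit".
- **SAP.** It does not mention interim analyses and has no primary efficacy section. Its intention-to-treat paragraph covers participants who complete the study.
- **What is absent.** Neither document gives an adjusted estimate, an interval for the PSQI difference, or a rule for participants between randomisation and Day 30 when a boundary is crossed.

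**The concern.** A group-sequential boundary protects the test. It does not protect the estimate. A trial that stops for benefit does so because the observed difference was large, so the ordinary difference at that moment is selected upward. Readers will set the result against the 3 points that Section 7.3 calls clinically relevant, and a true benefit below 3 could well be reported as above it. At the design effect an early stop is more likely than not, so this is not a rare case. Participants already randomised but not yet at Day 30 would supply data that played no part in the decision to stop, and the plan does not secure those data.

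**Working it through.** **Inputs.** The target difference is 3 and the SD 5 (Section 7.3: "assuming a 5-point standard deviation, the targeted 3-point reduction is equivalent to a 0.6 standardized effect"). There are 60 completers per arm at the end (Section 7.3) and looks at 20 and 40 per arm (Section 7.4). The one-sided error is 0.025 (Section 7.2). The outcome is baseline minus Day 30 PSQI, as Section 7.2 describes it in words.

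**The plan's own figure.** SE at 60 per arm = 5 × √(2/60) = 0.913, and 3/0.913 = 3.286. Power = Φ(3.286 − 1.960) = 90.8% (90.3% by the noncentral t). With the two looks added, simulated power is 90.3%. The stated 90% is reproduced.

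**Boundaries.** For three equally spaced looks at two-sided 0.05 the O'Brien-Fleming constant is 2.004, and the limit at n per arm is z = 2.004 × √(60/n). The smallest difference that crosses is z × 5 × √(2/n).

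| Completers per arm | z | SE | Smallest crossing difference |
|---|---|---|---|
| 20 | 3.471 | 1.581 | 5.49 |
| 40 | 2.454 | 1.118 | 2.74 |
| 60 | 2.004 | 0.913 | 1.83 |

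With t critical values the last column becomes 6.00, 2.81 and 1.85.

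**Ordinary difference after an early stop** (simulation, known SD 5, at least one million trials per scenario):

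| True difference | Trials stopping early for benefit | Mean ordinary difference in those | Bias over all trials | Naive 95% interval wholly above truth, all trials (nominal 2.5%) |
|---|---|---|---|---|
| 2.0 | 25% | 3.52 | +0.15 | 3.3% |
| 2.5 | 41% | 3.68 | +0.20 | 4.1% |
| 3.0 | 59% | 3.89 | +0.24 | 3.7% |

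A hand check at true 3.0: about 6% stop at the first look (mean 6.16) and 53% at the second (mean 3.64). (0.06 × 6.16 + 0.53 × 3.64)/0.59 = 3.90, which agrees.

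At true 2.0, 74% of early stops show 3 points or more. Counting every trial, the chance of an estimate of 3 or more is 21%, against 14% with a fixed 60 per arm.

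**Sensitivity** (assumed values). At true 2.0, SD 4 gives an early-stop mean of 2.94 with 34% at 3 or more, and SD 3 gives 2.44 with 17%. If nobody dropped out and the final analysis were at 120 per arm, the crossing differences would be 7.60 and 3.80. At true 2.0 about 5% would then stop early, with a mean of 4.28.

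**Including participants already randomised.** If m further completers per arm, unselected, join n at the stop, the pooled mean is (n × early mean + m × truth)/(n + m). Taking n = 40 at true 2.0, m = 10 gives (40 × 3.52 + 10 × 2.0)/50 = 3.22, and m = 20 gives (40 × 3.52 + 20 × 2.0)/60 = 3.01. Simulation, which also counts first-look stops, gives about 3.2 and 3.0. The share at 3 or more falls from 74% to 57% and 46%. The documents give no figure for m, so 10 and 20 are assumptions.

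**Which adjusted estimate.** The Whitehead estimate is the true value d at which the expected ordinary estimate equals the observed one. The simulated expectation is 3.498 at d = 3.25 and 3.762 at d = 3.50, so an observed 3.52 gives 3.25 + 0.25 × (3.52 − 3.498)/(3.762 − 3.498) = 3.27. In the same way 3.89 becomes 3.62. The stage-wise median-unbiased estimate hardly moves: at the second look 3.00 becomes 2.995 and 3.50 becomes 3.485, and at the first look it is unchanged. The stage-wise interval matters more for large results. For an observed 5.0 at the second look the ordinary lower limit is 5.0 − 1.96 × 1.118 = 2.81, and the stage-wise limit is 2.27.

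**The case against.** The strongest reply is that the conditional figures make the problem look larger than it is. Over all trials the bias is at most about a quarter of a point, first-look stops occur in only about 6% of trials even at the design effect, and interval error of 3.3–4.1% against 2.5% is modest. That is correct, and it limits the size of the point. It does not remove it, because the reader of a stopped trial sees only the conditional result.

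Several stronger readings do not hold:

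- *The trial's error rate or power is compromised.* This point gives no support for that. Section 7.2 says "In this way, the proposed test controls the one-sided type I error rate at 2.5" per cent, Section 7.4 names boundaries that allow for repeated looks, and the stated power is reproduced with them.
- *The device could be declared successful on an inflated 3 points.* Success is a p-value with the right direction. No rule requires the observed difference to reach 3, so crossing it affects interpretation only.
- *The plan states that the naive difference is reported after a stop.* It does not. That is inferred from the t-test and mean summaries and the absence of anything else. The ordinary 95% interval is likewise assumed.
- *A crossing forces a stop.* The boundaries are guidelines, and Section 12 lists circumstances that may justify termination.
- *Every early stop overstates.* The effect is an average. With SD 3 and a true 3.0, second-look stops average 2.76.

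One could also argue that the SAP's intention-to-treat rule already brings in later completers. It does not secure this, because Section 12 foresees that a termination may change participants' visit schedules, so they may never complete.

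**Conclusion.** The concern holds as a gap in estimation. A stop for benefit is permitted, and the plan is silent on the estimate, the interval and the participants still in follow-up. At SD 5 with a final analysis at 60 per arm, the ordinary difference after an early stop is on average about 1.5 points too high at true 2.0 (3.52 − 2.0) and 0.9 too high at true 3.0 (3.89 − 3.0). Over all trials the excess is +0.15 and +0.24. These figures assume the boundaries are followed, the SD is known, and only completers at the look enter the estimate. They shrink with a smaller SD. With a larger final sample, early stops become rarer but more selected. The matter should be settled before the first look, but it does not threaten the primary test.

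**What to change.** Add to Protocol Section 7.4 and to the SAP:

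1. If the trial stops for benefit at a look, everyone already randomised is followed to Day 30 under the blinded assignment and included in the reported PSQI difference. The result at the look is shown separately as the basis of the decision.
2. Beside the ordinary difference, report a bias-adjusted mean (for example Whitehead's) and a 95% confidence interval valid for the boundaries used, with those boundaries given as numbers. A stage-wise median-unbiased estimate alone is not enough, since it leaves the headline almost unchanged.

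The cost is a few sentences and standard group-sequential software, with no extra recruitment. The downsides are a somewhat less favourable estimate and up to 30 more days, plus the visit window, before the final result after a stop.

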## **9. Safety**

### **9.1. Risk/Benefit Assessment**

#### **9.1.1. Known Potential Risks**

There are no predicate devices used specifically to treat nightmares. However, there are many variations of over-the-counter applications and wearable devices that vibrate to signal the wearer. The same risks known to over-the-counter wearable fitness devices apply to this device.

The NW digital therapeutic is designed to interrupt during a nightmare, but not awaken the individual. The device may instead awaken, or incorrectly diagnose a nightmare and alarm (false positive). Therefore, worsening sleep quality is a potential risk of this device intervention.

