### **13.2. Study Records Retention**

The Office of Research Development/ Office of Research Oversight (ORD/ORO" Records Control Schedule Guideline (DAA-0015-2015-0004) states:

All Protocol Files related to the review and oversight of human subjects' research protocols submitted by principal investigators to the IRB shall have a cutoff at the end of the fiscal year after the research project has been completed or terminated. Records will be retained for 6 years after the cutoff.

Records include, but are not limited to, the application to the IRB; research protocol and amendments; case reports forms; informed consent template and HIPAA Authorization template; reports of adverse events, complaints, and deviations from IRB-approved protocol; data and safety monitoring reports; research findings to date; and all relevant documents and related correspondences between the IRB and the investigators in the review of an associated protocol.

No records will be destroyed without the written consent of the sponsor, if applicable.

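### Section 7.4 limits both interim looks to demographics and the primary endpoint, so an efficacy stop could be recommended with no scheduled reading of safety by arm

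*Protocol*

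**What the plan says.** Protocol Section 7.4 states: "The trial will incorporate two interim analyses after 20 and 40 participants in each arm have completed the first 30 days of the trial". It adds: "Statistical monitoring guidelines will be based on two-sided O'Brien-Fleming boundaries". It then limits the content: "The interim analyses will assess only patient demographics and primary endpoint". Section 7.4 does not define the primary endpoint, but Section 7.2 opens with "The primary hypothesis is that NW will improve sleep quality as measured by the Pittsburgh Sleep Quality index (PSQI) relative to sham", and the power calculation in Section 7.3 concerns PSQI alone.

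Safety is handled elsewhere. The Synopsis lists ESS and C-SSRS as primary safety outcomes. Section 7.5 calls ESS the primary and C-SSRS the secondary safety endpoint, and tests each by a one-sample t-test of change from Day 0 to Day 30 in the Active System. Section 9.1.1 accepts that "worsening sleep quality is a potential risk of this device intervention", because the device may wake the wearer or respond to a false positive.

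Section 12 lists circumstances that may warrant suspension or termination. They include demonstrated efficacy, the primary endpoint being met, futility, and "Determination of unexpected, significant, or unacceptable risk to participants". The SAP has no interim section.

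**The concern.** The word *only* makes this a stated restriction and not missing detail. The Schedule of Activities and Section 6.12 put ESS, C-SSRS, PHQ-9 and PSQI at the same Day 30 visit. For the participants who trigger each look, the safety data are therefore due at the same visit as the efficacy data, but the report leaves them out.

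Two things follow. First, a recommendation to stop for benefit could be made without the safety half of a trial whose stated aim is to establish both safety and efficacy. Second, the efficacy criterion in Section 12 has planned looks and a boundary, while the risk criterion has no scheduled by-arm analysis behind it. Sham participants move to Active at Visit 2, so the randomised comparison ends at Day 30. If the device raised sleepiness or suicide risk on average, the plan has no scheduled point during the trial at which that would be seen.

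**Working it through.** **1. The plan's own figure.** Inputs from Sections 7.2 to 7.4: difference 3, SD 5, 60 completers per arm, two-sided 0.05, looks at 20 and 40 per arm. The expected z at 60 per arm is 3 / (5 × √(2/60)) = 3.29. Fixed-sample power is 90.8% by the normal approximation and 90.3% by the t-test. With three-look O'Brien-Fleming boundaries at information 1/3, 2/3 and 1, the critical values are 3.47, 2.45 and 2.00, power is 90.3%, and the sample-size inflation factor is 1.016. The stated 90% power and negligible inflation both reproduce.

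**2. Is an early efficacy stop a realistic path?** The expected z is 3.29 × √(1/3) = 1.90 at look 1 and 3.29 × √(2/3) = 2.68 at look 2.
- Look 1: 1 − Φ(3.47 − 1.90) = 5.8%.
- By look 2 (joint calculation): 59.1%.

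This takes 60 per arm as the final analysis. If all 120 per arm completed, 40 per arm would be one third of the information. An O'Brien-Fleming critical value there is at least 1.96 / √(1/3) = 3.39, and the chance of crossing is at most about 1 − Φ(3.39 − 2.68) = 24%. At look 1 the critical value would be at least 1.96 / √(1/6) = 4.80, which adds almost nothing. Under the design effect, the chance of crossing by look 2 is therefore somewhere between just under a quarter and three fifths.

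**3. What would an ESS table show?** The documents give neither an SD for ESS change nor a harmful difference. Assume an SD of 3 to 5 points and a true Active excess of 2 points. Then SE = SD × √(2/n) and z = 2 / SE.

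| n per arm | SE, SD 3 | SE, SD 5 | z, SD 3 | z, SD 5 | chance z > 1.96 |
|---|---|---|---|---|---|
| 20 | 0.95 | 1.58 | 2.1 | 1.3 | 56% to 24% |
| 40 | 0.67 | 1.12 | 3.0 | 1.8 | 85% to 43% |

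The last column is Φ(z − 1.96), with z unrounded. The 1.96 is only a yardstick for visibility; no test is proposed.

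**4. Rare events.** With no events among n Active completers, the one-sided 95% upper limit for the event rate is 1 − 0.05^(1/n): 13.9% at n = 20 and 7.2% at n = 40. A by-arm table could show a marked imbalance in new ideation or behaviour, but could not rule out a small one.

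**5. Does anything else in the plan fill the gap?**
- Sections 6.12 to 6.14 and 9.1.3: C-SSRS and PHQ-9 item 9 trigger assessment of the individual. Site staff have no access to allocation (Section 6.4), so they cannot see an average difference.
- Sections 9.2.2 to 9.2.4: unanticipated problems, qualifying serious events and unanticipated adverse events go to the sponsor. This route carries events, not mean ESS or the distribution of C-SSRS.
- Section 7.4: the boundary is two-sided, so harm could be flagged, but only on PSQI.
- Section 7.5: the named ESS and C-SSRS tests are within the Active arm and come at the end.

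**The case against.** The strongest reply is that Section 7.4 governs only two formal efficacy analyses. A reader might infer that it forbids any by-arm safety review, or that nobody could make one. The documents do not support that. Event reports reach the sponsor, Section 9.2.4 describes sponsor evaluation of unanticipated adverse device effects, and Section 7.1 says unblinded NightWare programmers hold the allocation. What stands is narrower: no such review is scheduled, and the event route does not carry average ESS or C-SSRS.

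Other points in the plan's favour:
- Individual safeguards are substantial. C-SSRS at High excludes at entry, and a rise or a High rating at follow-up triggers immediate assessment. The gap concerns average excess, not the care of any one participant.
- PSQI is itself the sleep-quality measure, so a two-sided look at it partly covers the risk named in Section 9.1.1. The cover is partial, because Section 9.1.3 assigns that risk to ESS.
- The primary endpoint could be read to include ESS, which Section 7.5 calls the primary safety endpoint. The singular wording and the PSQI-only power text point the other way. C-SSRS and adverse events would be left out even then.
- Stopping is not automatic: Section 7.4 speaks of guidelines, and Section 12 of circumstances that may warrant it.

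Further inferences should be resisted. That the looks are by arm follows from testing Active against Sham, but Section 7.4 does not say who sees the results. The mention of "data and safety monitoring reports" in Section 13.2 belongs to a general retention list. It neither shows that a monitoring plan exists nor contradicts Section 7.4. It is also tempting to double the completers to count those randomised at each look. The 50% attrition is an upper limit applied to consented subjects, some of whom may fail eligibility before randomisation, so the documents give no reliable count of participants randomised or still to start.

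**Conclusion.** The point holds as a gap in scheduled review. Both interim looks exclude ESS, C-SSRS, PHQ-9 and adverse events by arm, an efficacy stop is possible at either, and nothing scheduled informs the Section 12 risk criterion by arm. Under the plan's own effect and SD, the chance of crossing the boundary by look 2 is about 59% if the final analysis is at 60 per arm, and at most about 24% if all 120 per arm complete.

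How much a safety table would reveal rests on the assumed 2-point ESS excess and SD of 3 to 5. On those values an average harm may be visible by the second look. A reader might infer that it would usually be seen, but at the upper SD the chance of exceeding 1.96 is 43%. The primary analysis, sample size and power are unaffected. The change is worth making because it is cheap and the data are already collected.

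**What to change.** Replace the restricting sentence in Section 7.4 with text to this effect:

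*Each interim analysis covers demographics and the PSQI comparison. Each interim report also tabulates by arm, for all randomised participants with data at the cut-off: ESS change from baseline; C-SSRS category and any new ideation or behaviour since baseline; PHQ-9 total and item 9; serious adverse events; and withdrawals with reasons. These tables are descriptive, carry no test and spend no alpha. The PhD biostatistician who performs the by-arm PSQI analysis prepares and reads them; blinded site investigators do not see them. They are read before any efficacy stop is recommended, and they inform the unacceptable-risk criterion in Section 12.*

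Naming the reader matters because Section 7.7 allows the Principal Investigator to carry out all analyses. Without that limit, more by-arm data could reach a blinded investigator. Define the primary endpoint in Section 7.4 as PSQI change at Day 30, and add a short matching interim section to the SAP.

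Cost: a few extra tables at each look and a small additional amount of by-arm data to keep confidential. No extra participants, visits or alpha, and no change to sample size or power.
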